While preliminary work is not necessary for a Planning Grant application (R34), our team has pilot data and expertise that is directly relevant to this application.

Development, feasibility and efficacy of the Tobacco Status Project (TSP). During her postdoctoral fellowship, [name] led a mixed-methods study to determine how young adult smokers would like to use Facebook to help change smoking behavior. About a third (31%) of survey respondents reported they would want to quit smoking using Facebook, and interest was greater among those more motivated to quit, who had made a quit attempt in the past year, and had previously used the Internet for assistance with a quit attempt (all $p<0.01$). In qualitative interviews, social support and convenience were identified as strengths of a Facebook intervention, while privacy was the main concern.⁴

[name] is currently funded with a five-year K23 career development award from NIDA to develop and test the feasibility and efficacy of Tobacco Status Project, combining Facebook contacts tailored to participants' readiness to quit smoking with a 12-week cessation program consisting of 7 state-of-the-art group cognitive-behavioral sessions occurring over Facebook text chat. A feasibility trial enrolled 79 young adults who formed 7 Facebook groups. Follow-up rates were 84% and 72% at 6 and 12 months, respectively, and reported 7-day abstinence was 21% at 6 months (9% biochemically-verified) and 18% at 12 months (9% verified).^{6,7} From baseline to 12-months, there was a significant increase in the proportion prepared to quit (13% to 46%, $p<.001$), 35% reduced their cigarette consumption by 50% or greater, and 67% reported a 24-hr quit attempt. Engagement in the intervention was high, with 92% participation in the full 3 month intervention and 61% commented on at least one post, with more commenting among those randomized to receive a personal monetary incentive.¹⁰⁹ Participants reported reading most of the Facebook posts (mean usability rating=3.3/4) and interactions from counseling sessions (3/4), thinking about what they read (3/4) and would recommend the program to others (3.3/4). Given low participation in CBT sessions (7 of 79 participated) but extremely high engagement (6/7 sessions attended on average) we incorporated the sessions directly into the Facebook groups for a larger efficacy trial currently underway.

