through the study's private group pages. If participants wish to have private study interactions with study staff they can do so at any time. Three-month follow-up assessments will be emailed to participants upon completion of treatment.

Informed consent, baseline and 3, 6, and 12 month assessments will be delivered using the online survey program Qualtrics, which is HIPAA-compliant, has been used often in medical research, and is being used successfully by [name] for her current Facebook intervention study. Verification of non-smoking status will be conducted for all participants reporting no smoking in the past 7 days at the post-test assessment using mailed saliva cotinine test kits and verified online as described in the **Measures** section. Participants will receive their choice of Amazon or Best Buy gift cards in the amount of \$20 for each 20-30 minute online survey, and a bonus \$20 for completing all assessments, for a total of \$100 possible compensation for participation. Amazon and Best Buy were chosen as retail outlets given their overwhelming popularity among a large choice of retailers given in [name] previous studies with young adult smokers.^{4, 111} Assessments will not be considered complete until staff receives verification of abstinence.

Measures.

Primary outcome (tobacco):

- **Biochemically-verified 7-day point prevalence abstinence from all tobacco products** will be assessed at 3, 6, and 12 months. Participants reporting no smoking in the past 7 days will be coded as abstinent from cigarettes. Those reporting 7-day abstinence will be mailed a saliva cotinine test kit, and record two pictures: one giving a saliva sample, and another of the test result. Participants with a salivary cotinine level <11 ng/ml, indicating nonsmoking,¹⁶³ will be considered confirmed nonsmokers. Biochemical verification is recommended in randomized trials with sample sizes under 500,¹⁶⁴ saliva cotinine test kits have been successfully mailed to participants in previous studies,¹⁶⁵ and [name] is using this method successfully in her K23 Facebook smoking cessation RCT with young adults (to date, 50% reporting 7-day abstinence have successfully completed biochemical verification). If participants indicate use of an electronic nicotine delivery-system to aid in smoking cessation, saliva cotinine and reported ENDS use will be recorded and reported separately from biochemically verified abstinence.

Secondary outcomes (tobacco):

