Feasibility analyses will examine four areas: **(1) Recruitment Efforts:** We will evaluate (a) length of time to recruit N=160 participants to enroll in the pilot trial, and (b) demographic, smoking, and drinking characteristics of those eligible and who enroll; **(2) Usability:** We will calculate mean responses to Likert scale items of the usability measure and any sections with lower than median values will indicate changes should be made before future investigations take place. **(3) Implementation of biochemical verification of tobacco abstinence:** We will determine the proportion of participants in each condition reporting 7-day point prevalence abstinence at 3-month follow-up that completes a saliva cotinine test and the rate of discordance between saliva cotinine results and self-report. **(4) Attrition:** We will track the number and proportion of participants that completes each follow-up assessments and compare these numbers to previous Internet cessation trials (attrition as high as 75%^{52, 53, 199-201}).

Analyses for Specific Aim 2: Preliminary efficacy.

Descriptive statistics will summarize sample characteristics and the extent of intervention delivery in each group. We will examine treatment condition and baseline descriptive characteristics as predictors of

attrition at trial end (month 3) and propose to control for predictors of attrition as covariates in model testing. Missing data will be minimized through online assessment. When subjects do not complete online assessments, they will be re-contacted through Facebook or email to obtain missing information. For each test related to smoking, two sets of outcome analyses will be conducted - one with all participants who are maintained in the study, and another based only on biochemically verified smoking abstinence rates to allow for direct comparison of findings with the research literature.

Primary outcome: To test for the effects of treatment condition on smoking abstinence at 3- through 12-months, we will estimate and test a mixed-effects logistic regression model. Abstinence status will be examined as 7-day point prevalence. The independent variables are TSP versus TSP+ALC plus variables that are related to abstinence such as cigarettes per day, differ by condition at baseline or predict attrition. We will use multiple imputation procedures to impute missing data.

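### Cotinine-kit completion and discordance are evaluated only at month 3, although verified abstinence is the primary outcome at 3, 6 and 12 months

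*Combined protocol and SAP*

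**What the plan says.** C.9, Specific Aim 2: Feasibility, area (3), evaluates verification through the proportion in each condition "reporting 7-day point prevalence abstinence at 3-month follow-up that completes a saliva cotinine test" and through "the rate of discordance between saliva cotinine results and self-report". The discordance clause names no visit of its own. On the natural reading it falls under the same 3-month limit. Area (4) of the same list follows attrition at every follow-up.

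C.8, Measures, Primary outcome (tobacco), says that biochemically verified 7-day abstinence "will be assessed at 3, 6, and 12 months". C.9 models abstinence from 3 through 12 months and plans, for each smoking test, a second set of analyses restricted to verified abstinence.

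C.8, Procedures, describes verification for everyone "reporting no smoking in the past 7 days at the post-test assessment using mailed saliva cotinine test kits", in the singular, and adds: "Assessments will not be considered complete until staff receives verification of abstinence".

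Two sets of earlier figures bear on verification. For the ongoing trial, C.8 states that "50% reporting 7-day abstinence have successfully completed biochemical verification". For the feasibility trial, the preliminary-work section before C.3 states: "reported 7-day abstinence was 21% at 6 months (9% biochemically-verified) and 18% at 12 months (9% verified".

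**The concern.** A verified abstainer must report abstinence, return a kit and pass the test. When about half of reported abstainers are verified, return and test result move the verified rate about as much as quitting does. The feasibility analysis is the one place where the plan examines that step, and it looks at one visit of three. Month 3 is the end of treatment. Months 6 and 12 come after the daily posts and weekly sessions have stopped, so kit return at month 3 cannot be assumed to hold later.

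Two things are at stake. First, whether mailed verification is feasible is a named Aim 2 result meant to inform a larger trial, and it would rest on very few people. Second, a change in verified abstinence between visits, or a difference between arms at a later visit, could not be split into smoking, kit return and failed tests.

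**Working it through.** **Inputs.** N = 160 and 30% attrition (C.8, Sample size and power analysis). Reported and verified abstinence were 21% and 9% at 6 months, and 18% and 9% at 12 months (feasibility trial). Verification was completed by 50% of reported abstainers (ongoing trial). No month-3 self-report rate is given, so it is assumed and varied.

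**1. The plan's own figure.** 160 × (1 − 0.30) = 112 retained, and 112 / 2 = 56 per arm. This reproduces the plan.

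**2. Verified share of reported abstainers.** 9/21 = 43% at 6 months and 9/18 = 50% at 12 months, taking each pair of percentages on a common denominator. These ratios mix kit return with test result.

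**3. People behind the month-3 estimate, per arm.**
- At 18%: 56 × 0.18 = 10.1. At 21%: 56 × 0.21 = 11.8.
- With a wider assumed range of 10% to 30%: 5.6 to 16.8.

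**4. Precision at 50% completion (Clopper-Pearson, 95%).**
- 5 of 10: 19% to 81%.
- 6 of 12: 21% to 79%.
- Three visits, with 21% assumed at month 3: 12 + 12 + 10 = 34 kit occasions per arm. For 17 of 34: 32% to 68%. This treats repeat kits from one person as independent, so the true interval is somewhat wider.

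**5. Share of reported abstainers at the two omitted visits.** (0.21 + 0.18) / (r + 0.21 + 0.18), where r is the month-3 rate. This gives 65% at r = 21%, and from 80% (r = 10%) to 57% (r = 30%).

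**6. Effect of kit return on the verified rate.** Assume that self-report is constant at s = 21%, every returned kit agrees with self-report, and return p falls from 50% to 30%. The fall is illustrative and has no source in the documents.
- *Unreturned kit coded as smoking:* s × p = 0.21 × 0.50 = 10.5%, falling to 0.21 × 0.30 = 6.3%.
- *Unreturned kit coded as missing, rate among observed cases:* s × p / (1 − s × (1 − p)) = 0.105 / 0.895 = 11.7%, falling to 0.063 / 0.853 = 7.4%. An imputation model that ignores self-report would do little to correct this, because only reported abstainers can go missing in this way.
- *Unreturned kit coded as missing, with self-report in the imputation model:* the rate can stay at 21%, so no shift need occur.

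C.9 states that missing data will be multiply imputed but gives no imputation model. No section says whether an unreturned kit is smoking or missing.

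**The case against.** The strongest case on the other side has six parts.

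- **A reader might infer that two-thirds of the verification data go unused.** The documents do not support that. Month-6 and month-12 results feed the primary outcome and the verified-only analyses. They are left out of one feasibility summary. Two-thirds counts visits, not data.
- **A reader might infer that falling kit return would appear as relapse.** That depends on the coding, which is unstated. The rule that an assessment stays incomplete without verification, together with multiple imputation, points at least as much to missing data. Nor do the plan's own longitudinal figures show a decline: 43% at 6 months and 50% at 12 months, on small numbers.
- **A reader might infer bias in TSP versus TSP+ALC.** Drift that is equal in both arms affects the time trend and the number of events, not the arm contrast. The contrast is at risk mainly if return differs by arm, and the documents give no reason to expect that.
- **Other analyses give a partial signal.** A fall in return would widen any gap between the two outcome sets, and unreturned kits may appear in the retention counts. This stands only in part. The first outcome set is not labelled as self-report, and neither source separates an unreturned kit from a failed test or a missed survey.
- **Single-visit cells stay small after the change.** This stands. Reporting by visit leaves about 12 people per cell, and 7/12 against 5/12 gives Fisher p = 0.68. The gain is description at each visit and a tighter pooled estimate, not a test of trend or of arm difference.
- **This is a pilot, and checking kit logistics at the end of treatment is a defensible choice.** That lowers the priority of the point. It does not explain why attrition is followed at every visit and verification at one.

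**Conclusion.** The mismatch is real and minor. The plan states a month-3 evaluation of kit completion, and on the natural reading of discordance, for an outcome verified at three visits. Using all three raises the data behind this feasibility result from about 12 to about 34 kit occasions per arm. That narrows the interval at 50% completion from 21-79% to about 32-68%. These sizes assume 56 retained per arm at each visit, 21% reported abstinence at month 3, feasibility-trial rates later, and independent repeats.

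A spurious shift in verified abstinence is possible but not demonstrated. It depends on the coding of unreturned kits and on what the imputation model contains. Bias in the arm comparison, and loss of the later results from the trial, are not supported. Sample size and the primary model do not change.

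**What to change.** In C.9, Feasibility, area (3), name the 3, 6 and 12 month follow-ups in place of the 3-month follow-up alone. Then:

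- report kit completion and discordance separately, by visit and by arm, with a pooled estimate per arm whose standard error is clustered on participant;
- place these beside the reported and verified abstinence rates at each visit;
- state whether an unreturned kit is coded as smoking or as missing and, if missing, whether self-report is in the imputation model;
- reconcile the single post-test assessment in C.8, Procedures, with verification at all three visits.

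The cost is a few sentences and a few table columns, with no new participants. It requires no new data provided kits are sent at all three visits, as the primary outcome definition implies.

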Final content for The [name] In sessions will be informed by the results of the focus groups and generated by [name] and [name] with collaboration from [name]. The [name] In sessions will be delivered by [name], who has also published in the area of alcohol use among young adults,^{154, 155} and a fellow in the UCSF Clinical Psychology Training Program who will both be supervised by [name]. With approximately 16 groups total (8 in each study condition, 4 Ready, 4 Not Ready, 10 members each on average), each therapist will conduct The [name] In sessions in 8 groups (2 Ready/2 Not Ready in each study condition).

Monetary Incentive for Engagement. Analyses of our TSP feasibility trial showed that a monetary incentive increased engagement in the Facebook intervention for all those who had some basic level of engagement (at least one Facebook comment).¹⁰⁹ In the RCT currently underway, groups are randomized to three different monetary incentive structures (daily, weekly, monthly) or no incentive. Although results are not final, preliminary analyses with 310 participants in the TSP condition in 10 TSP groups complete through 6/5/2015 (3 daily, 3 weekly, 1 monthly, 3 no incentive) indicate that any incentive is associated with higher engagement than no incentive (75% vs. 67% commenting at least once) and engagement is highest among those receiving an incentive in a weekly basis (82%). Thus in the present study, we will tally posts weekly and offer all participants a \$20 giftcard at the end of the intervention if they comment on all Facebook posts during the time period.

Nicotine Replacement Therapy (NRT).

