Sample size and power analysis. The sample N of 160 was set primarily for practical and clinical reasons and not driven by estimated effect sizes or hypothesis testing. We expect to have representation (although not equal) among males and females, and across ethnic groups consistent with our current trial of TSP. We also expect to have representation across levels of smoking and drinking, and readiness to quit using both substances. We anticipate an attrition rate of 30% at 3, 6, and 12 months, yielding a final sample size of 112 (56 in each group), enabling us to compare groups on primary and secondary outcomes at each timepoint. This will also generate an effect size estimate that will be useful for powering a larger trial.

A goal of 6 participants will be recruited per week during the 6-month recruitment period, which is in line with recruitment for our feasibility trial and current RCT.¹¹¹

Procedures. Participants will be recruited through Facebook and Craigslist advertisements, using a similar strategy to that of focus group and usability-testing. All advertisements will provide a link to the study’s website, with eligibility questions. If respondents are eligible, then they will be taken to the informed consent webpage. Participants consenting to participate in the study will be asked to verify age by sending proof through email or social media, a process used successfully in [name] previous research. Verified participants will be emailed a baseline assessment. Those completing the baseline assessment will be randomized to either TSP, or TSP+ALC, stratified based on readiness to quit smoking (Ready in the next 30 days, Not Ready in 30 days) and smoking pattern (daily vs. non-daily), variables known to be related to outcomes and addressed by the intervention.¹⁶¹ A stratified random assignment program will be developed in consultation with [name], and used currently in [name] RCT of TSP. All participants will then be assigned to a secret group tailored to their condition and readiness to quit tobacco. Groups will begin when there are approximately 12 participants enrolled, as that has been deemed the optimal number based on analyses of engagement in our previous work.^{109, 162} Groups will receive one social media post daily for 90 days and weekly “The [name] In” counseling sessions managed

[figure not shown]

Figure 2. Participant flow through the study

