Secondary outcomes: For secondary outcomes we will estimate and test mixed effects logistic and multinomial regression models for longitudinal ordinal response data to model secondary outcomes for tobacco use and alcohol use across time (3, 6, 12 months): 1) reduction of cigarettes by 50% or more (y/n), 2) tobacco or alcohol quit attempt (y/n; 2 models), 3) readiness to quit tobacco and alcohol (Precontemplation, Contemplation, Preparation, Action/Maintenance; 2 models); and 4) commitment to abstinence (no goal, intermediary goal, complete abstinence). In parallel, mixed effects linear regression models will model the following continuous outcomes over time: 1) past 30 day HED; 2) average number of drinks per week in the past 30 days, 3) severity of alcohol use (AUDIT-C score); 4) desire to cut down tobacco and alcohol use (1 to 10; 2 models); and 5) sum of days using either tobacco or alcohol in the past 30 days. Independent variables in all models will be treatment condition, abstinence status, and covariates identified as relevant to smoking characteristics in the literature.

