Analyses for Specific Aim 3 (Engagement and Patterns of Social Interaction). Analyses will use Facebook data extracted from the private groups we develop on Facebook using the Facebook API. All data will be de-identified and transferred to **[name]**, expert on social media analytics at Drexel University, for analysis. The data will include the content of the posts and comments, the activity of each participant (e.g., number, content, and time of all comments), and interactions among participants. We will determine patterns of engagement, type of posts that are most “engaging” to participants, and relate engagement to smoking and drinking outcomes using three main analyses: **(1) Patterns of engagement:** Total number of “likes” and comments to Facebook groups over the 3 month intervention period will be tallied for each group (TSP, TSP+ALC), and the non-parametric Kruskal-Wallis ANOVA will compare likes and comments in each intervention and include covariates of baseline characteristics (readiness to quit tobacco/alcohol, daily/non-daily smoking status, gender) and group membership; a social network analysis will examine the interaction patterns among different types of users with which participants engage in each intervention; a content analysis will evaluate the content of comments within each group and observe differences among the two groups; **(2) Success of specific posts:** To evaluate which posts are most successful at engaging participants, Drs. [name] and [name] will collaborate on coding posts based on content type (e.g., alcohol/tobacco, Motivational Interviewing, specific CBT skills). Specific codes will be determined upon design of the TSP+ALC intervention). ANOVA will then be used to examine likes and comments by post type within each group (TSP, TSP+ALC) **(3) Engagement and outcomes:** We will compare TSP and TSP+ALC groups on the relationship between intervention engagement (FB comments) and primary tobacco and alcohol outcomes (abstinence, heavy drinking days) at the end of the 3 month intervention period. Logistic regression will be used to analyze tobacco abstinence, and linear regression for days of heavy drinking at 3 months, controlling for any baseline differences in treatment groups. Kruskal-Wallis tests will evaluate the effect of incentive condition (personal, altruistic, no incentive) on comments to the Facebook group, in both the full sample and only those who made at least one comment to the group to address likely skewed data.

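### The efficacy models name no random effect for the Facebook groups in which treatment is delivered, and the primary model's covariates are chosen after the data are seen

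*Combined protocol and SAP*

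**What the plan says.** **Delivery.** Under C.8 Procedures, individuals are randomised with stratification by readiness to quit and by daily or non-daily smoking. Then, "All participants will then be assigned to a secret group tailored to their condition and readiness to quit tobacco". C.5 plans "approximately 16 groups total (8 in each study condition, 4 Ready, 4 Not Ready, 10 members each on average". Each group receives daily posts for 90 days and weekly live counselling sessions. Section B presents the social connection among group members as part of the intervention.

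**Efficacy models.** For abstinence from 3 to 12 months, C.9 states "we will estimate and test a mixed-effects logistic regression model". The independent variables are treatment condition "plus variables that are related to abstinence such as cigarettes per day, differ by condition at baseline or predict attrition". The preceding paragraph examines predictors of attrition at month 3 and says the team will "propose to control for predictors of attrition as covariates in model testing". On missing data: "We will use multiple imputation procedures to impute missing data". The secondary outcomes use mixed-effects logistic, multinomial and linear models: "Independent variables in all models will be treatment condition, abstinence status, and covariates identified as relevant to smoking characteristics in the literature".

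**Where group appears.** The only analysis that mentions group membership is the Aim 3 comparison of likes and comments, which is to "include covariates of baseline characteristics (readiness to quit tobacco/alcohol, daily/non-daily smoking status, gender) and group membership".

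**Purpose.** C.8 sets N = 160 on practical grounds. It expects the trial to yield an effect size estimate that will help to power a larger trial.

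**The concern.** Members of one Facebook group see the same discussion, meet the same counsellor and influence one another for three months. Similar outcomes within a group are therefore plausible, and the design partly aims for them. Each group lies wholly within one arm, so between-group variance enters the arm comparison even though individuals were randomised.

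The term mixed-effects does not settle the matter. With visits at 3, 6 and 12 months, its most natural reading is a participant intercept for repeated measures. An analyst could follow C.9 to the letter and leave the Facebook group out. Intervals would then be too narrow, and the effect estimate passed on to the larger trial would look more precise than it is, with no between-group variance reported beside it.

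The second and smaller issue is that two of the three routes by which a covariate enters the primary model depend on trial data: an observed baseline difference, for which no threshold is given, and prediction of month-3 attrition. The model cannot be written down before those data are seen.

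**Working it through.** **Inputs from the documents.** 160 randomised and 30% attrition (C.8); about 16 groups, 8 per arm, mean size 10 (C.5); groups start at about 12 (C.8). In the earlier TSP feasibility trial, 6-month abstinence was 21% reported and 9% verified. In the ongoing TSP trial, verified abstinence at 3 months was 7.1%.

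**Assumptions.** ICC 0, 0.02, 0.05 or 0.10; two-sided 5% tests; one visit; equal groups.

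**1. The plan's own figure.** 160 × 0.70 = 112, or 56 per arm, as C.8 states. Spread over 16 groups this is 112/16 = 7 retained per group.

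**2. Standard errors.** The design effect is DE = 1 + (m − 1) × ICC, and the correct standard error is √DE times one that ignores groups. For a continuous outcome, the true error of a nominal 5% test that ignores groups is 2 × [1 − Φ(1.96/√DE)]. With m = 7:

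| ICC | DE | √DE | True error, continuous outcome |
|---|---|---|---|
| 0 | 1.00 | 1.000 | 5.0% |
| 0.02 | 1 + 6 × 0.02 = 1.12 | 1.058 | 6.4% |
| 0.05 | 1 + 6 × 0.05 = 1.30 | 1.140 | 8.6% |
| 0.10 | 1 + 6 × 0.10 = 1.60 | 1.265 | 12.1% |

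Simulation of null trials with 8 groups of 7 per arm gave 6.3–6.5%, 8.3–8.7% and 12.1–12.4% at the three non-zero ICCs.

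Group size matters moderately. If groups start at 12 and keep 70% (m = 8.4), √DE is 1.071, 1.170 and 1.319. With all 10 members of a group retained, it is 1.086, 1.204 and 1.378.

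**3. Abstinence.** The planned model is logistic, so the relevant interval is a Wald interval for the log odds ratio. Simulated null trials (beta-binomial, 8 groups of 7 per arm, groups ignored, 100,000 trials per cell; a trial with no quitters in one arm counted as non-significant):

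| ICC | Wald error at 9% | Coverage at 9% | Wald error at 21% |
|---|---|---|---|
| 0 | 2.2% | 97.8% | 4.5% |
| 0.02 | 2.9% | 97.1% | 5.8% |
| 0.05 | 4.2% | 95.8% | 7.7% |
| 0.10 | 6.2% | 93.8% | 11.1% |

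Only the change from the ICC 0 row is due to grouping. At 9% the Wald method is conservative to begin with because events are few: from 0.071 × 56 = 4.0 to 0.09 × 80 = 7.2 quitters per arm.

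**4. Covariate rule.** Simulated null trials with a continuous outcome (160 randomised, 112 analysed, 16 independent baseline covariates, 6,000 trials per setting) applied one baseline-difference threshold once:
- Covariates unrelated to outcome: error 5.2, 5.1 and 5.2% at thresholds of 5, 10 and 20%.
- Covariates explaining an assumed 20% of variance: error 4.7, 4.7 and 4.2%.

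The rule, applied once, does not inflate error. What remains is that the threshold and the resulting covariate list are left open.

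**The case against.** **The size rests on assumption.** The documents give no ICC, at 0 nothing is lost, and the figures are for one visit while the plan is longitudinal. This stands. The omission from the text is certain; its size is not.

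**This is a pilot.** N was not set by hypothesis testing and the section is titled preliminary efficacy. This stands too, and it limits the severity. It does not remove the point, because the effect estimate is meant for use in powering a larger trial.

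**The primary outcome is barely affected.** A reader might infer that ignoring groups inflates false positives for verified abstinence. The documents do not support that for the planned log-odds model: near 9% the Wald error stays below 5% at ICC 0.02 and 0.05. The effect is clear for the continuous drinking outcomes and for abstinence near 21%, the self-reported rate in the feasibility trial.

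**The strata may already be covered.** C.8 describes readiness and smoking pattern as related to outcomes, and C.9 admits variables related to abstinence. Read together, these could bring both in. So the strata are not excluded; they are simply not named. Leaving them out would be conservative.

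**The Aim 3 wording is not conclusive.** The sentence that mentions group membership also uses group to mean arm. Facebook group is the likelier reading because treatment is already the comparison, but the point does not depend on it.

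**A follow-on trial could be underpowered.** A reader might infer this. The documents do not say that such a trial would ignore an ICC, and its comparator is given only as an example, so no power figure is attached here.

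**Conclusion.** The point holds as a cheap improvement. C.9 does not say that the efficacy models include a Facebook-group effect, and a participant-only model would satisfy the text. If the ICC is above 0, that model understates standard errors. With 7 retained per group, they should be about 6, 14 and 26% larger at ICC 0.02, 0.05 and 0.10. The consequence is largest for the continuous drinking outcomes. For verified abstinence near 9%, coverage erodes from above nominal and drops below 95% only near ICC 0.10.

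The covariate rule is the lesser matter. It might be read as a source of false positives, but applied once it is not. It leaves discretion to the analyst and leaves the two randomisation strata unnamed.

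Confidence is high that the group term is not specified and moderate about the size of the effect, which depends on the assumed ICCs, equal groups and a single visit.

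**What to change.** - **Random effects.** State participant and Facebook-group random intercepts in the primary and secondary efficacy models. Use a small-sample correction with degrees of freedom based on the actual number of groups. In a group-level analysis with an intercept, arm and readiness, that is 16 − 3 = 13 for 16 groups, or 13 − 3 = 10 if groups of about 12 give 13 (160/12 = 13.3).
- **Sparse abstinence.** Pre-specify a simple group-level analysis of proportions on arm, adjusted for readiness, for use if the group variance cannot be estimated.
- **ICC.** Report it with its interval and say that it is imprecise. At a true 0.05 with 7 retained per group, 95% of estimates for a continuous outcome would fall between about −0.08 and 0.21.
- **Covariates.** Fix readiness and daily/non-daily smoking, plus baseline cigarettes per day where events allow. Delete selection by baseline difference. Move predictors of attrition to the imputation model, and include the Facebook group there as well.

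The cost is some analysis-plan wording and one short extra analysis. Group and strata are already recorded. The downsides are slightly wider intervals and fewer degrees of freedom.
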